4.2.4 Medical History

Medical history will be coded using the Medical Dictionary for Regulatory Activities (MedDRA) [Version 23.0 (or a later version if updated during the study)]. The number and percentage of subjects with any medical history will be summarized for the SSO by system organ class (SOC) and preferred term (PT) overall. The number and percentage of subjects with any medical history will be summarized for the SSR by system organ class (SOC) and preferred term (PT) overall.

4.2.5 Previous and Concomitant Medications

Medications received prior to or concomitantly with study treatment will be coded using the WHO Drug Dictionary [Version March 2020 (or a later version if updated during the study)], Anatomical Therapeutic Chemical (ATC) Classification codes.

Prior medications and concomitant medications are as defined as follows:

Prior medications are those taken with a stop date prior to the first dose date of study treatment during the open-label correction period.

Concomitant medications during the open-label correction period are those with a start date anytime before the first dose date of study treatment during the randomized placebocontrolled period and a stop date on or after the first dose of study treatment during the openlabel correction period. Concomitant medications during the randomized placebo-controlled period are those with a stop date on or after the first dose date of study treatment during the randomized placebo-controlled period.

If a medication cannot be classified as "prior" or "concomitant during the open-label correction period" or "concomitant during the randomized placebo-controlled period" after applying imputation rules for missing/incomplete dates, it will be classified as concomitant during the randomized placebo-controlled period.

Concomitant medications during the open-label correction and randomized placebo-controlled periods will be further categorized by those allowed and disallowed. Disallowed concomitant medications are defined in the CSP Section 6.8 as starting on RAASi therapy during the trial (ATC level 2 code C09) or sodium-glucose transport protein 2 inhibitor therapy. Furthermore, several medications which are described as restricted will also be included as disallowed concomitant medications.

Prior medications, allowed/disallowed concomitant medications during the open-label correction period and allowed/disallowed concomitant medications during the randomized placebo-controlled period will be listed together. Allowed/disallowed concomitant medications during the open-label correction period will be summarized using the SSO and presented in total. Allowed/disallowed concomitant medications during the randomized placebo-controlled period will be summarized separately by treatment group and overall using the SSR.

The number and percentages of subjects using each medication will be displayed together with the number and percentage of subjects using at least one medication within each therapeutic class (ATC-Level 2), chemical subgroup (ATC-Level 4), and generic term.

4.2.6 Measurements of Study Treatment Compliance

The percentage compliance for SZC and placebo is calculated for each analysis period as:

100*actual sachets taken/expected sachets taken

, where:

Actual sachet taken is defined as:

Sum of the sachets taken throughout the respective analysis period

And the expected sachets taken throughout the respective analysis period is derived using the study intervention and drug dispensation records to calculate the number of sachets expected accounting for changes to the prescribed dosage level (from 10g three times daily to 5g every other day) and the unit dose strength dispensed (5g and 10g sachets).

The percentage compliance for SZC and placebo will be calculated separately for the openlabel and placebo-controlled periods and will be summarized descriptively overall using the SSO and treatment group using the SSR respectively.

Furthermore, for SZC/placebo the number and percentage compliance will be presented separately for the open-label and placebo-controlled periods using the SSO and SSR respectively with the following compliance categories:

- <50%
- $\geq 50\%$ to < 80%
- $\geq 80\%$ to < 120%
- ≥120%

Furthermore, at each study visit during the open-label and placebo-controlled periods there will be a categorical summary of the number and percentage of subjects assigned to each dose of SZC/placebo (e.g. 5g every other day, 5g daily, 10g daily, 15g daily).

4.2.7 Efficacy

To control for type I error, a hierarchical testing procedure will be followed when formally testing primary and secondary efficacy analysis endpoints. The hierarchical testing procedure will follow a stepwise algorithm where each endpoint is only formally tested if the preceding null hypothesis is rejected (p<0.05). The first secondary endpoint will only be formally tested if the null hypothesis for the primary endpoint is rejected at p<0.05. Endpoints which are not formally tested will have a p-value displayed when one can be calculated. However, a footnote will indicate that the "P-value is descriptive only due to a previous endpoint in the hierarchical testing procedure failing to have the null hypothesis rejected (p≥0.05). The final order for hierarchical testing will be the order displayed below.

4.2.7.1 Primary Efficacy Analysis

The primary efficacy endpoint is the occurrence (yes/no) of patients having normal sK+ (between 3.5 and 5.0 mmol/L inclusive) on Day 29 (Visit 7) without rescue treatment for hyperkalemia at any point during the randomized phase in the SZC versus placebo arm. Patients with missing sK+ will have these imputed as described in section 3.3.1. The number and percentage of subjects who achieved a response (Yes, No, Non-evaluable) will be summarized by randomized treatment group in the FAS.

The occurrence will be compared between treatment groups in the FAS using a logistic regression model (excluding non-evaluable responses) including response as the dependent variable and randomized treatment as an independent factor, it will be tested using a two-sided

alpha = 0.05. The common odds ratio will be derived together with the two-sided 95% confidence interval.

Documentation will be provided to check the underlying assumptions for the logistic regression model. Standardized residuals will be presented in a scatter plot by alphanumerical subject ID. Subjects with standardized residuals > 3.0 will be listed. Influential observations on the regression coefficients will be detected by calculating Cook's D statistic (In SAS applied with proc reg with the plots=cooksd option) and presented in a diagnostic plot by alphanumerical subject ID. Subjects with Cook's D statistic > 4/sqrt(n) will be listed.

Estimand Attributes

In line with ICH E9 (R1) addendum, 5 attributes (treatment, population, endpoint, intercurrent events, and population-level summary) have been specified to translate the primary and key secondary efficacy objectives into treatment effects that are to be estimated (estimands).

Endpoint:

• Hyperkalaemia response, defined as an observed sK+ within 3.5-5.0 mEq/L at Day 29 (Visit 7)

Population:

• All subjects who achieve normokalemia at the end of the open-label correction phase, and are randomized

Treatment:

• SZC or Placebo. Patients with $sK+ \ge 6.0 \text{ mmol/L}$ will be managed with rescue therapy employing local standard of care.

Intercurrent Event Strategy:

- Discontinuation of treatment (Treatment policy strategy, i.e. regardless of the intercurrent event)
- Use of rescue therapy for hyperkalaemia at any point during the randomized placebocontrolled period (Composite variable strategy, i.e. considered to be non-response).
- Use of rescue therapy for low bicarbonate at any point during the randomized placebocontrolled period (Treatment policy strategy, i.e. regardless of the intercurrent event).
- Death prior to Day 29 (Visit 7) (Composite variable strategy, i.e. considered to be non-response).
- Subject lost to follow-up prior to Day 29 (Visit 7) (Hypothetical strategy, i.e. assume response is not evaluable).
- Subject with no sK+ or POCT K measurement at visit 6 or visit 7 (Hypothetical strategy, i.e. assume response is not evaluable).

Population Level Summary:

• Odds ratio of the proportion of responders in the SZC treatment group compared to the placebo group.

4.2.7.2 Primary Efficacy Analysis – Sensitivity Analyses

Three sensitivity analyses will be pre-specified to be conducted for the primary efficacy endpoint. Upon review of the trial data, additional post-hoc or subgroup analyses may be performed.

- Primary analysis as described above. In addition to randomized treatment, the originally specified logistic regression model would have included: race, gender, age at baseline (<65, ≥65), CKD stage at baseline (3, 4), diabetes status (Yes, No), POCT bicarbonate level at entry (16-18, 19-20), POCT type (i-STAT, Piccolo) and baseline use of RAASi therapy (Yes, No) as independent factors. Due to the early termination of the study only POCT type will be included as an independent factor.
- (ii) Primary analysis as described above but conducted in the PPS.
- (iii) The intercurrent event strategy will be altered to describe the treatment effect in a COVID-19 pandemic-free world.

- Discontinuation of treatment not related to the COVID-19 pandemic (Treatment policy strategy, i.e. regardless of the intercurrent event).
- Discontinuation of treatment related to the COVID-19 pandemic (Hypothetical strategy, i.e. assume response is missing).
- Use of rescue therapy for hyperkalaemia at any point during the randomizedwithdrawal period (Composite variable strategy, i.e. considered to be nonresponse).
- Use of rescue therapy for low bicarbonate at any point during the randomized placebo-controlled period (Treatment policy strategy, i.e. regardless of the intercurrent event).
- Death prior to Day 29 (Visit 7) not related to the COVID-19 pandemic (Composite variable strategy, i.e. considered to be non-response).
- Death prior to Day 29 (Visit 7) related to the COVID-19 pandemic (Hypothetical strategy, i.e. considered to be non-response).
- Subject lost to follow-up prior to Day 29 (Visit 7) irrespective of relationship to COVID-19 pandemic (Hypothetical strategy, i.e. assume response is not evaluable).
- Subject with no sK+ or POCT K measurement at visit 6 or visit 7 irrespective of relationship to COVID-19 pandemic (Hypothetical strategy, i.e. assume response is not evaluable).

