6 CHANGES OF ANALYSIS FROM PROTOCOL

Due to the early termination of this study all sensitivity analyses described in section 4.2.7.4, subgroup analyses described in section 4.2.7.5 and the interim analysis described in section 5 will not be conducted due to insufficient sample size.

7 **REFERENCES**

FDA. FDA Guidance on Conduct of Clinical Trials of Medical Products during COVID-19 Pandemic: Guidance for Industry, Investigators, and Institutional Review Boards. https://www.fda.gov/media/136238/download. Accessed 25 May 2021. Herson, J. and Wittes, J., 1993. The use of interim analysis for sample size adjustment. Drug Information Journal, 27(3), pp.753-760.

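### In the pandemic-free sensitivity analysis of the primary endpoint, the rule for COVID-19-related death contradicts its own strategy label

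*SAP*

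**What the plan says.** SAP section 4.2.7.2 announces three sensitivity analyses of the primary endpoint. The third states its aim as follows: "The intercurrent event strategy will be altered to describe the treatment effect in a COVID-19 pandemic-free world". It then lists how each intercurrent event is handled. The lines that matter here are:

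- COVID-19-related discontinuation: "Discontinuation of treatment related to the COVID-19 pandemic (Hypothetical strategy, i.e. assume response is missing"
- death from other causes: "Death prior to Day 29 (Visit 7) not related to the COVID-19 pandemic (Composite variable strategy, i.e. considered to be non-response"
- COVID-19-related death: "Death prior to Day 29 (Visit 7) related to the COVID-19 pandemic (Hypothetical strategy, i.e. considered to be non-response"
- loss to follow-up, and absence of any usable potassium value at Visits 6 and 7: each is handled "irrespective of relationship to COVID-19 pandemic (Hypothetical strategy, i.e. assume response is not evaluable"

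The primary estimand in section 4.2.7.1 makes no distinction by cause of death: "Death prior to Day 29 (Visit 7) (Composite variable strategy, i.e. considered to be non-response". The primary model is a "logistic regression model (excluding non-evaluable responses".

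Section 6 lists what early termination removed: "all sensitivity analyses described in section 4.2.7.4, subgroup analyses described in section 4.2.7.5 and the interim analysis described in section 5 will not be conducted". Section 4.2.7.2 is not on that list.

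**The concern.** A hypothetical strategy asks what the outcome would have been had the event not happened. Scoring the event as a failure is a composite strategy. The COVID-19 death line names the first and prescribes the second. The explanation that follows the label is the part a programmer would implement, and it matches the rule for deaths from other causes.

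What is at stake is the meaning of one supportive analysis. If a COVID-19 death occurred and the line were coded literally, the report would describe the analysis as removing pandemic effects while that death still counted as a treatment failure, exactly as in the primary analysis. Two programmers could also code the same patient differently. Someone who stopped treatment because of COVID-19 and then died of it before Day 29 meets the discontinuation line (missing) and the death line (non-response), and no order of precedence is given.

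**Working it through.** **Step 1: compare the rules.**

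| Event | Primary estimand (4.2.7.1) | Analysis (iii) (4.2.7.2) | Rule changed? |
|---|---|---|---|
| Discontinuation, COVID-19-related | treatment policy | hypothetical: missing | yes |
| Discontinuation, other | treatment policy | treatment policy | no |
| Death, COVID-19-related | composite: non-response | labelled hypothetical: non-response | label only |
| Death, other | composite: non-response | composite: non-response | no |
| Lost to follow-up, or no potassium value | hypothetical: not evaluable | hypothetical: not evaluable | no |

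Two lines carry a pandemic-specific strategy. Only the discontinuation line changes how a patient is scored.

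**Step 2: see how the SAP uses the label elsewhere.** The hypothetical strategy is named 23 times across sections 4.2.7.1 to 4.2.7.3. The other 22 uses set the response to missing or not evaluable; this line alone sets it to non-response. One of the 22 concerns death itself: for secondary endpoint #7, death before Day 29 is hypothetical and not evaluable.

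**Step 3: check that the analysis is still planned.** Section 6 cancels sections 4.2.7.4, 4.2.7.5 and 5. Section 4.2.7.2 was itself revised for early termination, since analysis (i) was cut to one added covariate (POCT type), and (iii) was left in place.

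**Step 4: illustrate the size.** The SAP gives no number of COVID-19 deaths, no number randomized at termination and no expected response rate for the primary endpoint. The only anchor is the planned 68 per arm (section 1.3), which reproduces. With rates 0.175 and 0.39, mean 0.2825, two-sided alpha 0.05 and power 80%:

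n = [1.960 × √(2 × 0.2825 × 0.7175) + 0.842 × √(0.175 × 0.825 + 0.39 × 0.61)]² / 0.215² = 67.6, so 68 per arm. Then 136 / 0.92 = 147.8, so 148 enrolled.

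For one arm with r responders among n patients and one COVID-19 death among the others, the rate is r/n if the death is a non-response and r/(n − 1) if it is not evaluable. The difference is r/[n(n − 1)].

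- Assumed 41 responders of 68: 41/68 = 60.3% against 41/67 = 61.2%, a difference of 0.9 points.
- Upper limit, all 67 others responding: 67/68 = 98.5% against 67/67 = 100%, a difference of 1.5 points.

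The estimand's summary is an odds ratio. Assume 68 per arm, 48 responders on SZC and 31 on placebo had nobody died, and COVID-19 deaths unrelated to response. With deaths not evaluable, the expected odds ratio stays at (48/20)/(31/37) = 2.86. With d deaths scored as non-response, expected responders in that arm fall to r(68 − d)/68 while the denominator stays at 68:

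| COVID-19 deaths, SZC / placebo | Odds ratio, non-response | Odds ratio, not evaluable |
|---|---|---|
| 0 / 0 | 2.86 | 2.86 |
| 1 / 1 | 2.80 | 2.86 |
| 2 / 2 | 2.74 | 2.86 |
| 3 / 0 | 2.48 | 2.86 |
| 0 / 3 | 3.11 | 2.86 |

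With 54 and 27 assumed responders instead, the odds ratio is 5.86 with deaths not evaluable, and 4.78 (3 / 0) or 6.31 (0 / 3) with deaths as non-response.

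**Step 5: choose between missing and not evaluable.** Section 3.3.1 fills a missing Visit 7 potassium from Visit 6 or an unscheduled value in between. A patient who died of COVID-19 between those visits could therefore be imputed if the line said only that the response is missing. Section 4.2.7.1 removes non-evaluable responses from the model, so that term fixes the handling.

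**The case against.** The strongest reply is that this is a drafting slip with an obvious intended meaning. The label, the decision to give COVID-19 deaths a separate line, and the stated aim all point to the hypothetical reading. Only the closing words point the other way, and they repeat those of the line directly above. That is plausible, and it means the plan should not be read as a deliberate choice to count COVID-19 deaths as failures. It does not settle the matter, because nothing in the SAP says which half of the line governs.

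The reply on consequence also stands. The analysis is supportive and outside the testing hierarchy, the randomized period is about four weeks, and without a COVID-19 death before Day 29 both readings give the same result.

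A reader might infer that the analysis as a whole cannot answer its question. The documents do not support that, since the COVID-19 discontinuation line departs from the primary rule in the intended direction. A reader might also infer that, in a small terminated trial, the line produces false reassurance about robustness. That would need the number randomized and at least one COVID-19 death, and the SAP gives neither.

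**Conclusion.** The point holds for the death component of analysis (iii) and no further. The line contradicts its own label and, taken literally, makes the split of deaths by cause inoperative, so for deaths the analysis does not describe a setting without the pandemic. The primary analysis and its error control are unaffected.

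The size is unknown and may be zero. Under the assumptions shown, one COVID-19 death at 68 per arm moves that arm's response rate by about 1 percentage point (at most 1.5), and one death per arm moves an odds ratio of 2.86 to 2.80. The larger shifts in the table need three deaths, all in one arm. The shift in a response rate would be greater in smaller arms. Severity is minor: an internal inconsistency to clear before the analysis is programmed.

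**What to change.** In section 4.2.7.2 (iii), keep the hypothetical label on the COVID-19 death line and replace non-response with not evaluable, as in the loss-to-follow-up line of the same list. The patient then leaves the model under section 4.2.7.1 and is not imputed from Visit 6 under section 3.3.1. Add a sentence that the same rule applies to a patient with both COVID-19-related discontinuation and COVID-19-related death. Leave the composite rule for other deaths as it is.

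If non-response is what the sponsor wants, relabel the line as composite and do not describe the analysis as pandemic-free with respect to deaths.

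Either way the cost is one or two lines of SAP text. No sample size, primary result or testing order changes.

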4.2.7.3 Secondary Efficacy Analyses

1 Mean change in serum bicarbonate from baseline (Day 1) to Day 29 (Visit 7) in SZC versus placebo arm.

Serum bicarbonate will be summarized and listed in the FAS using the visits of Baseline (Visit 1), randomization (Visit 3) and Day 29 (Visit 7). Patients with missing serum bicarbonate values at visit 7 will have these imputed with serum bicarbonate values from visit 6 if available, as described in section 3.3.2. The mean change in serum bicarbonate from baseline (Day 1) will be analyzed using analysis of covariance (ANCOVA) analyses at the significance level 5% (2-sided), with randomized treatment as main effect and baseline bicarbonate as covariate. For patients needing rescue treatment for low bicarbonate, the last value of the POCT bicarbonate during the randomized period prior to rescue treatment will be analyzed. The analysis will be based on the FAS.

Documentation will be provided on the underlying assumptions for the ANCOVA model. This will include a check that the residuals are approximately normally distributed by plotting a histogram of the residuals for the model as well as a Shapiro-Wilk test which will reject the null hypothesis that the residuals are normally distributed if p<0.05. Secondly, the homogeneity of variance will be visually checked through an inspection of a plot of residuals versus predicted values from the model. Finally, the homogeneity of slopes will be determined by conducting an ANCOVA analysis where the dependent variable is Day 29 (Visit 7) serum bicarbonate and the independent variables are randomized treatment group, baseline serum bicarbonate. If p>0.05 for the interaction term, then we will accept the homogeneity of the treatment slopes.

Estimand Attributes

Endpoint:

• Change in serum bicarbonate at Day 29 (Visit 7) from baseline

Population:

• All subjects who achieve normokalemia at the end of the open-label correction phase, meet inclusion/exclusion criteria and are randomized

Treatment:

• SZC or Placebo. Patients with $sK+ \ge 6.0 \text{ mmol/L}$ will be managed with rescue therapy employing local standard of care.

- Discontinuation of treatment (Treatment policy strategy, i.e. regardless of the intercurrent event)
- Use of rescue therapy for hyperkalaemia at any point during the placebo-controlled period (Treatment policy strategy, i.e. regardless of the intercurrent event).

- Use of rescue therapy for low bicarbonate at any point during the randomized controlled period (While on treatment strategy, e.g. last observation carried forward).
- Death prior to Day 29 (Visit 7) (While on treatment strategy, e.g. last observation carried forward).
- POCT bicarbonate measurement unavailable for Visits 6 and 7 (Hypothetical strategy, assume response is missing).
- Subject lost to follow-up prior to Day 29 (Visit 7) (Hypothetical strategy, assume response is missing).

- Least squares mean estimate in the SZC treatment group compared to the placebo group.
- 2 Occurrence (yes/no) of patients having an increase in serum bicarbonate of ≥2 mmol/L on Day 29 (Visit 7) from baseline without need for rescue treatment for low bicarbonate in SZC versus placebo arm.

For secondary efficacy endpoints #2 - #7 the number and percentage of subjects with the endpoint (Yes, No, Non-evaluable) will be summarized by randomized treatment group in the FAS. Patients with missing sK+ or serum bicarbonate values at visit 7 will have these imputed as described in sections 3.3.1 and 3.3.1. The occurrence of each secondary efficacy endpoint will be compared between treatment groups in the FAS using a logistic regression model including the binary response endpoint as the dependent variable and randomized treatment as an independent factor, it will be formally tested using a two-sided alpha = 0.05 if the hierarchical testing strategy supports conducting a formal hypothesis test. The common odds ratio will be derived together with the two-sided 95% confidence interval.

For each secondary efficacy endpoint #2 - #7, documentation will be provided to check the underlying assumptions for the logistic regression model. Standardized residuals will be presented in a scatter plot by alphanumerical subject ID. Subjects with standardized residuals > 3.0 will be listed.

Endpoint:

• Serum bicarbonate response, defined as an increase from baseline in serum bicarbonate value ≥2 mmol/L at Day 29 (Visit 7)

Population:

• All subjects who achieve normokalemia at the end of the open-label correction phase, meet inclusion/exclusion criteria and are randomized

Treatment:

• SZC or Placebo. Patients with $sK+ \ge 6.0 \text{ mmol/L}$ will be managed with rescue therapy employing local standard of care.

- Discontinuation of treatment (Treatment policy strategy, i.e. regardless of the intercurrent event)
- Use of rescue therapy for hyperkalaemia at any point during the placebo-controlled period (Treatment policy strategy, i.e. regardless of the intercurrent event).
- Use of rescue therapy for low bicarbonate at any point during the randomized controlled period (While on treatment strategy, e.g. last observation carried forward).
- Death prior to Day 29 (Visit 7) (Composite variable strategy, i.e. considered to be non-response).
- Subject lost to follow-up prior to Day 29 (Visit 7) (Hypothetical strategy, i.e. assume response is not evaluable).
- Subject with no POCT or central laboratory bicarbonate measurements at visit 6 or visit 7 (Hypothetical strategy, i.e. assume response is not evaluable).

- Odds ratio of the proportion of responders in the SZC treatment group compared to the placebo group.
- 3 Occurrence (yes/no) of patients having an increase in serum bicarbonate of ≥3 mmol/L on Day 29 (Visit 7) from baseline without need for rescue treatment for low bicarbonate in SZC versus placebo group.

Endpoint:

• Serum bicarbonate response, defined as an increase in serum bicarbonate value ≥3 mmol/L at Day 29 (Visit 7) from baseline

Population:

• All subjects who achieve normokalemia at the end of the open-label correction phase, meet inclusion/exclusion criteria and are randomized

Treatment:

• SZC or Placebo. Patients with $sK+ \ge 6.0 \text{ mmol/L}$ will be managed with rescue therapy employing local standard of care.

- Discontinuation of treatment (Treatment policy strategy, i.e. regardless of the intercurrent event)
- Use of rescue therapy for hyperkalaemia at any point during the placebo-controlled period (Treatment policy strategy, i.e. regardless of the intercurrent event).
- Use of rescue therapy for low bicarbonate at any point during the randomized controlled period (While on treatment strategy, e.g. last observation carried forward).
- Death prior to Day 29 (Visit 7) (Composite variable strategy, i.e. considered to be non-response).

- Subject lost to follow-up prior to Day 29 (Visit 7) (Hypothetical strategy, i.e. assume response is not evaluable).
- Subject with no POCT or central laboratory bicarbonate measurements at visit 6 or visit 7 (Hypothetical strategy, i.e. assume response is not evaluable).

- Odds ratio of the proportion of responders in the SZC treatment group compared to the placebo group.
- 4 Occurrence (yes/no) of patients having a normal sK+ (between 3.5 and 5.0 mmol/L inclusive) on Day 29 (Visit 7) and an increase in serum bicarbonate of ≥3 mmol/L on Day 29 (Visit 7) from baseline without need for rescue treatment for hyperkalemia or low bicarbonate.

Endpoint:

• Hyperkalaemia response, defined as an observed sK+ within 3.5-5.0 mEq/L at Day 29 (Visit 7) and serum bicarbonate response, defined as an increase in serum bicarbonate value of ≥3 mmol/L at Day 29 (Visit 7) from baseline.

Population:

• All subjects who achieve normokalemia at the end of the open-label correction phase, meet inclusion/exclusion criteria and are randomized

Treatment:

• SZC or Placebo. Patients with $sK+ \ge 6.0 \text{ mmol/L}$ will be managed with rescue therapy employing local standard of care.

- Discontinuation of treatment (Treatment policy strategy, i.e. regardless of the intercurrent event)
- Use of rescue therapy for hyperkalaemia at any point during the placebo-controlled period (While on treatment strategy, e.g. last observation carried forward).
- Use of rescue therapy for low bicarbonate at any point during the randomized controlled period (While on treatment strategy, e.g. last observation carried forward).
- Death prior to Day 29 (Visit 7) (Composite variable strategy, i.e. considered to be non-response).
- Subject lost to follow-up prior to Day 29 (Visit 7) (Hypothetical strategy, i.e. assume response is not evaluable).
- Subject with no sK+ or POCT K measurement at visit 6 or visit 7 (Hypothetical strategy, i.e. assume response is not evaluable).
- Subject with no POCT or central laboratory bicarbonate measurements at visit 6 or visit 7 (Hypothetical strategy, i.e. assume response is not evaluable).

- Odds ratio of the proportion of responders in the SZC treatment group compared to the placebo group.
- 5 Occurrence (yes/no) of patients having serum bicarbonate ≥22 mmol/L on Day 29 (Visit 7) without need for rescue treatment for low bicarbonate in SZC versus placebo group

Endpoint:

• Serum bicarbonate response, defined as a serum bicarbonate value of ≥22 mmol/L at Day 29 (Visit 7)

Population:

• All subjects who achieve normokalemia at the end of the open-label correction phase, meet inclusion/exclusion criteria and are randomized

Treatment:

• SZC or Placebo. Patients with $sK+ \ge 6.0 \text{ mmol/L}$ will be managed with rescue therapy employing local standard of care.

Intercurrent Event Strategy:

- Discontinuation of treatment (Treatment policy strategy, i.e. regardless of the intercurrent event)
- Use of rescue therapy for hyperkalaemia at any point during the placebo-controlled period (Treatment policy strategy, i.e. regardless of the intercurrent event).
- Use of rescue therapy for low bicarbonate at any point during the randomized controlled period (While on treatment strategy, e.g. last observation carried forward).
- Death prior t Day 29 (Visit 7) (Composite variable strategy, i.e. considered to be non-response).
- Subject lost to follow-up prior to Day 29 (Visit 7) (Hypothetical strategy, i.e. assume response is not evaluable).
- Subject with no POCT or central laboratory bicarbonate measurements at visit 6 or visit 7 (Hypothetical strategy, i.e. assume response is not evaluable).

Population Level Summary:

- Odds ratio of the proportion of responders in the SZC treatment group compared to the placebo group.
- 6 Occurrence (yes/no) of patients having a normal sK+ (between 3.5 and 5.0 mmol/L inclusive) on Day 29 (Visit 7) and a serum bicarbonate of \geq 22 mmol/L on Day 29 (Visit 7) without need for rescue treatment for low bicarbonate or hyperkalemia

Endpoint:

• Hyperkalaemia response, defined as an observed sK+ within 3.5-5.0 mEq/L at Day 29 (Visit 7) and serum bicarbonate response, defined as a serum bicarbonate value of ≥22 mmol/L at Day 29 (Visit 7).

Population:

• All subjects who achieve normokalemia at the end of the open-label correction phase, meet inclusion/exclusion criteria and are randomized

Treatment:

• SZC or Placebo. Patients with $sK+ \ge 6.0 \text{ mmol/L}$ will be managed with rescue therapy employing local standard of care.

Intercurrent Event Strategy:

- Discontinuation of treatment (Treatment policy strategy, i.e. regardless of the intercurrent event)
- Use of rescue therapy for hyperkalaemia at any point during the placebo-controlled period (While on treatment strategy, e.g. last observation carried forward).
- Use of rescue therapy for low bicarbonate at any point during the randomized controlled period (While on treatment strategy, e.g. last observation carried forward).
- Death prior to Day 29 (Visit 7) (Composite variable strategy, i.e. considered to be non-response).
- Subject lost to follow-up prior to Day 29 (Visit 7) (Hypothetical strategy, i.e. assume response is not evaluable).
- Subject with no sK+ or POCT K measurement at visit 6 or visit 7 (Hypothetical strategy, i.e. assume response is not evaluable).
- Subject with no POCT or central laboratory bicarbonate measurements at visit 6 or visit 7 (Hypothetical strategy, i.e. assume response is not evaluable).

Population Level Summary:

- Odds ratio of the proportion of responders in the SZC treatment group compared to the placebo group.
- 7 Occurrence (yes/no) of patients needing rescue treatment for low bicarbonate (serum bicarbonate from $POCT \le 15 \text{ mmol/L}$) during the randomized phase between SZC and placebo.

Endpoint:

• Use of rescue treatment for low bicarbonate, where low bicarbonate is defined as a serum bicarbonate value of ≤15 mmol/L during the randomized placebo-controlled period

Population:

• All subjects who achieve normokalemia at the end of the open-label correction phase, meet inclusion/exclusion criteria and are randomized

Treatment:

• SZC or Placebo. Patients with $sK+ \ge 6.0 \text{ mmol/L}$ will be managed with rescue therapy employing local standard of care.

Intercurrent Event Strategy:

- Discontinuation of treatment (Treatment policy strategy, i.e. regardless of the intercurrent event)
- Use of rescue therapy for hyperkalaemia at any point during the placebo-controlled period (Treatment policy strategy, i.e. regardless of the intercurrent event).
- Death prior to Day 29 (Visit 7) (Hypothetical strategy, i.e. assume response is not evaluable).
- Subject lost to follow-up prior to Day 29 (Visit 7) (Hypothetical strategy, i.e. assume response is not evaluable).
- Subject with no POCT or central laboratory bicarbonate measurements at visit 6 or visit 7 (Hypothetical strategy, i.e. assume response is not evaluable).

Population Level Summary:

• Odds ratio of the proportion with rescue treatment for low bicarbonate in the SZC treatment group compared to the placebo group.

